#### Clinical development of PD-1 inhibitors

PD-1 is a negative regulator of T-cell activity that limits the activity of T cells at a variety of stages of the immune response when it interacts with its two ligands PD-L1 and PD-L2. PD-1 is primarily believed to inhibit effector T-cell activity in the effector phase within tissues. This pathway is likely important in the tumor microenvironment where PD-L1 expressed by tumors interacts with PD-1 on T cells to suppress T-cell effector function by limiting T-cell receptor localization to the immunologic synapse at the site of target engagement.

[figure not shown]

[figure not shown]
Figure 4: The Role of PD-1 in Early T-Cell Activation

Source: Postow et al, JCO 2015

Anti-PD-1 antibodies have robust clinical activity, with a response rate of 17% in patients with metastatic melanoma in a Phase 1 multi-center study. This was confirmed in several larger studies. In 107 patients with advanced melanoma who were treated with nivolumab, the ORR was 31% with a median OS of 16.8 months. Among patients who had an objective response, the median response duration was two years. In another trial of patients who had previously received ipilimumab, patients who received pembrolizumab had a similar ORR of 26%. 

Most recently, 834 patients were enrolled in a randomized Phase 3 study of ipilimumab vs pembrolizumab, dosed either every 2 or 3 weeks. The ORR was 33.7% with pembrolizumab every 2 weeks, 33.9% every 3 weeks and 11.9% with ipilimumab (P<.001). The 12-month OS rates were 74.1%, 68.4%, and 58.2%, respectively. The sum of these data lead to the FDA approval of both pembrolizumab and nivolumab for the treatment of metastatic melanoma.

Figure 5: Kaplan-Meier Curves for Overall Survival and Progression Free Survival Demonstrating a Survival Benefit in Patients Treated with Pembrolizumab Dosed Every Two or Three Weeks vs Ipilimumab

Source: Robert et all, 2015

#### Clinical development of combination checkpoint blockade

Strong preclinical rationale for the combined evaluation of combined CTLA-4 and PD-1 pathway blockade was provided by basic immunologic observations, which supported the notion that CTLA-4 and PD-1 are non-redundant pathways for regulation of T-cell responses. This hypothesis was first tested in a Phase 1 clinical trial of nivolumab plus ipilimumab in advanced melanoma. The ORR in the concurrent treatment group was 40%, but 53% in the patients who were treated with the maximum doses with an acceptable level of adverse effects. This initial finding was confirmed in two Phase 3 trials in previously untreated patients.

#### 4.3 Rationale

Checkpoint inhibitors enhance antitumor immunity by blocking negative regulators of T-cell function that exist both on immune cells and on tumor cells. There are 2 classes of checkpoint

blockade currently FDA approved, CTLA-4 antibodies and PD-1 antibodies. CTLA-4 and PD-1 are non-redundant pathways for the regulation of T-cell responses; CTLA-4 is believed to regulate immune responses early in T-cell activation, while PD-1 is believed to inhibit T-cell effector function within the tissues. Interestingly, both agents are thought to decrease regulatory T cells in the tumor microenvironment, which may dampen a cytotoxic T cell response.

Ipilimumab blocks CTLA-4 and has a demonstrated survival benefit for patients with previously untreated advanced melanoma in two Phase 3 trials. Nivolumab is a PD-1 antibody and has demonstrated a survival benefit both in patients with ipilimumab-refractory advanced melanoma  and in patients with previously untreated metastatic melanoma. The two agents have demonstrated a synergistic effect, consistent with their various pathways, in a large clinical trial of combination checkpoint blockade with an overall response rate 57.6%.

PD-1 inhibitors are increasingly being utilized in the first-line treatment setting for metastatic melanoma due to a more favorable response rate and side effect profile compared to ipilimumab. However, as a result, there is no current standard of care for the 60% of patients who will have progressive or relapsed disease after single agent PD-1 blockade. While the response rate of PD-1 inhibitors in patients previously treated with ipilimumab is well known, there is no data for the efficacy of ipilimumab as a second agent. Moreover, combination checkpoint blockade has also never been tried in this population.

We hypothesize that by administering a CTLA-4 antibody to this population of PD-1 inhibitor pre-treated patients, we will activate alterative T-cell activation pathways and deplete regulatory T cells in the tumor microenvironment, thus increasing immune activation and resulting in clinical efficacy. We are interested in administering ipilimumab both as a single agent and in combination with nivolumab to explore whether dual checkpoint blockade synergy is as active in a pre-treated population as in a treatment-naïve population. In addition, given the elevated toxicity rates associated with combination checkpoint blockade, it is important to assess toxicity profiles in both single and combined immunotherapy approaches in this pre-treated population.

Thus, we propose this randomized, parallel single arm, 2-stage Phase 2 study to assess response rates to ipilimumab alone and in combination with nivolumab in participants who have progressed after anti-PD-1 therapy.

#### 5 STUDY OBJECTIVES AND ENDPOINTS

#### 5.1 Study Objectives

#### **5.1.1** Primary Objective

The primary objective is to assess response rates of combination ipilimumab/nivolumab and ipilimumab alone in participants previously treated with a PD-1 inhibitor by Week 18 of therapy.

#### 5.1.2 Secondary Objectives

The Secondary Objectives are:

• To assess clinical benefit of combination ipilimumab/nivolumab and ipilimumab alone

- To evaluate time to treatment failure and OS for each arm
- To assess safety and tolerability of ipilimumab alone and in combination with nivolumab in previously treated participants.

# **5.1.3** Exploratory Objectives

- To evaluate peripheral lymphocyte phenotype changes throughout treatment
- To evaluate changes in quantities of myeloid derived suppressor cells (MDSCs), defined as CD14+HLA-DR $^{low}$  cells, and  $T_{reg}$  cells, defined as CD4+FOX3P+ cells, throughout treatment
- To evaluate nCounter immune profiling of the tumor before treatment
- To explore tumor neoepitopes and mutational burden via whole gene and exome sequencing on pre-treatment tumor biopsy and correlation with clinical response
- To stratify clinical response rate by PD-L1 expression on pre-treatment biopsies
- To evaluate the tumor immune microenvironment on pre- and on-treatment tumor biopsies.

## 5.2 Study Endpoints

## 5.2.1 Primary Endpoint

The primary endpoint of this study is the response to combination ipilimumab/nivolumab and Ipilimumab alone at Week 18 defined as having achieved a complete response or partial response (PR) as measured by Response Evaluation Criteria in Solid Tumors (RECIST) v1.1 criteria or a PR/complete response at any time prior to Week 18.

## 5.2.2 Secondary Endpoints

The secondary endpoints are as follows:

- Disease control rate (DCR) by RECIST v1.1 criteria of overall tumor burden at Week 12 and Week 18. DCR is defined as participants who achieve stable disease (SD), PR or complete response.
- Time to treatment failure and OS up to two years
- Safety and tolerability measured via metrics such as laboratory tests, vital signs, physical examinations as well as toxicity as graded by Common Terminology Criteria for AEs (CTCAE) v4.0.

# **5.2.3** Exploratory Endpoints

The exploratory endpoints of this study are as follows:

- All research samples for exploratory endpoints will be analyzed at a Parker Institute for Cancer Immunotherapy selected testing center. Please see Appendix 3 for further information
- Peripheral lymphocyte phenotype changes throughout treatment, including Treg cells, defined as CD4+FOX3P+ cells, will be expressed using descriptive statistics at pre and post treatment time points. These will be assessed via flow cytometry of peripheral blood mononuclear cells (PBMCs).
- Changes in quantities of MDSCs, defined as CD14+HLA-DRlow cells, throughout treatment will be expressed using descriptive statistics at pre and post treatment time points.

- nCounter immune profiling of the tumor before treatment will be expressed using descriptive statistics at pre and post treatment time points and will be correlated with clinical response also using logistic regression models.
- Tumor neoepitopes and mutational burden will be correlated with clinical response also using logistic regression models.
- Summary statistics will be generated and differences between mutation burden or neoantigen score as they relate to PD-L1 expression.
- Immunohistochemistry (IHC) will be used to assess PD-L1 expression on both immune cells and tumor cells. PDL-1 expression will be assessed pretreatment and on-treatment. A participant will be PD-L1 + if >1% of cells express PD-L1. If response data permit, the tumor positivity of PD-L1 expression will be compared in the pre- and post-treatment biopsies using a Wilcoxon signed rank test.
- Pre- and on- treatment PD-L1 expression and will be correlated with clinical response also using logistic regression models.
- IHC will be used to quantify cytotoxic and Tregs, including stains for CD3, CD4, CD8, FOXP3, ICOS and Lag3. Associations from pre to post treatment will be assessed using the Wilcoxon signed rank test for paired comparisons (e.g., the continuous measure, density of cells per high powered field).

#### 6 INVESTIGATIONAL PLAN

## 6.1 Description of Overall Study Design and Plan

This is a multi-center, randomized, Phase 2 study of ipilimumab vs ipilimumab plus nivolumab in participants previously treated with a PD-1 inhibitor by Week 18 of therapy.

There will be 2 treatment arms in this study.

**Arm A**: Participants will receive combination checkpoint blockade with ipilimumab and nivolumab.

**Arm B**: Participants in this arm will receive ipilimumab alone.

A Simon 2-stage design will be implemented in each arm, allowing for early stopping for futility. Participants who are eligible will be required to have a pre-treatment biopsy and then will be randomized to either ipilimumab alone or ipilimumab in combination with nivolumab. Participants will be required to have an on-treatment biopsy within 14±5 days of their first dose of treatment. Participants will receive treatment for up to 4 cycles followed by observation phase.

The primary objective is to determine the response rate of combination ipilimumab/nivolumab and ipilimumab alone in participants previously treated with a PD-1 inhibitor by Week 18 of therapy. The total planned accrual is 12 participants in each arm. Participants will be assessed for the primary endpoint at 18 weeks. They will then be followed for TTF and OS for up to 2 years.

Secondary objectives include assessment of tolerability of ipilimumab and combination checkpoint blockade in previously treated participants as well as assessment of OS and time to treatment failure.

## 6.1.1 Study duration

Participants on both arms will receive treatment for up to 4 cycles and then be observed for up to 2 years. After 2 years, all participants will go off study.

#### 6.1.2 Randomization

Randomization will be managed centrally using an interactive voice response (IVR) system. Participants will be randomized following their pre-treatment biopsy at Screening/Baseline Visit. Participants will be stratified based on their previous response to PD-1 therapy (primary refractory vs progressive disease) and melanoma subtype. The primary refractory and progressive disease cohorts are defined in Section 7.1 (inclusion criteria number 4).

Figure 6 illustrates randomization schema:

Ipilimumab once every 3 weeks (4 doses) 0 3 6 ġ Week 12 Week 18 CT Scan CT Scan R Nivolumab once every 3 a Screening weeks (4 doses) n OBSERVE d 0 m Ipilimumab once every 3 Week weeks (4 doses) iz Mandatory e Biopsy 0 3 6 9 within 14 days of treatment Mandatory Biopsy within 14 days of dose 1 of treatment

Figure 6: Simplified randomization schema

Note: The on-treatment biopsy has a window of  $\pm 5$  days.

## 6.2 Discussion of Study Design

This is a multi-center, randomized, parallel single arm, 2-stage Phase 2 study of ipilimumab and combined checkpoint blockade with ipilimumab and nivolumab in participants with unresectable Stage III or Stage IV melanoma who have previously received monotherapy with a PD-1 inhibitor with progression of disease or relapsed disease.

Checkpoint blockade has emerged as an effective therapeutic strategy for participants with advanced stage melanoma. Checkpoint inhibitors enhance antitumor immunity by blocking negative regulators of T-cell function that exist both on immune cells and on tumor cells. There are two classes of checkpoint blockade currently FDA approved, CTLA-4 antibodies and PD-1 antibodies. Ipilimumab blocks CTLA-4 and nivolumab is a PD-1 antibody. In this study, participants will be administered ipilimumab both as a single agent and in combination with nivolumab to explore whether dual checkpoint blockade synergy is as active in a pre-treated population as in a treatment-naïve population.

A total of 24 participants will be enrolled in this study. All participants will be followed up to 2 years after receiving the last dose of study drug.

#### 7 SELECTION AND WITHDRAWAL OF PARTICIPANTS

Participants will be recruited by their medical, surgical, and radiation oncologist who encounter them in the clinical setting. The clinical trial will be listed on the clinicaltrials.gov website and on the institution's website. Participants will be identified through internal referrals and external referrals by Medical and Surgical Oncologists nationally and internationally. Participants will also be approached by the institution's co-investigators. Every effort will be made to maximize recruitment of participants, including women and minorities. The target population of participants include those who have previously received monotherapy with a PD-1 inhibitor with progression of disease or relapsed disease. Participants must meet the inclusion and exclusion criteria; no exceptions will be made for enrollment.

#### 7.1 Inclusion Criteria

All participants must meet all of the following criteria at screening and baseline to participate in the study:

- 1. AJCC (2009) Stage IV cutaneous melanoma or Stage III cutaneous, acral or mucosal melanoma that is judged inoperable. Participants with a history of uveal melanoma are not eligible.
- 2. Measurable disease, defined as at least one lesion that can be accurately measured in at least one dimension (longest diameter to be recorded) as >20 mm with conventional techniques or as >10 mm with computerized tomography (CT) scan. Participants must have at least one measurable lesion by RECIST and a separate lesion amenable to biopsy.
- 3. Histologic proof of melanoma reviewed and confirmed by the enrolling site.
- 4. Previous treatment with a PD-1 or PD-L1 inhibitor with documented progression of disease on most recent CT scan. Progression of disease is defined as 1) the appearance of a new measurable lesion (>10 mm) on cross-sectional imaging or physical examination OR 2) enlargement of previously detected lesions on two consecutive imaging studies OR 3) enlargement of a previously detected lesion with correlative symptomatology on one cross-sectional imaging study. Participants remain eligible if they had a previous response to a PD-1 inhibitor, including participants who had a complete response, PR or SD. Any participant who had refractory or relapsed disease is eligible for study enrollment. Treatment populations are defined in Section 12.
- 5. Participants who received adjuvant PD-1 therapy who then develop measurable disease are eligible. However, they must have received their last dose of PD-1/PD-L1 blockade within two months of enrollment in this study. They will be stratified with participants who have primary progressive disease.
- 6. Life expectancy of greater than 3 months.
- 7. Age  $\geq$  18 years old.
- 8. ECOG performance status = 0 or 1 or Karnofsky Performance Status equivalent
- 9. Participants must have adequate organ and marrow function as defined below:
  - a. White blood cells (WBC) >2, 000/mcL
  - b. Absolute neutrophil count >1,500/mcL
  - c. Platelets >100,000/mcL

- d. Hemoglobin > 9.0 g/dL
- e. Total bilirubin  $\leq 1.5$  X institution's upper limit of normal
- f. Aspartate aminotransferase (AST) (serum glutamic oxaloacetic transaminase)/alanine aminotransferase (ALT) (serum glutamic pyruvic transaminase)  $\leq 2.5$  X institution's upper limit of normal for participants with no concurrent liver metastases,  $OR \leq 5$  X institution's upper limit of normal for participants with concurrent liver metastases
- g. Serum creatinine < 1.5x OR creatinine clearance of at least 40
- 10. Women of childbearing potential must have a negative serum pregnancy test within 24 hours prior to the start of study drug. A woman of childbearing potential is defined as any female who has experienced menarche and who has not undergone surgical sterilization (hysterectomy or bilateral oophorectomy) or is not postmenopausal. Menopause is defined clinically as 12 months of amenorrhea in a woman over age 50 in the absence of other biologic or physiologic causes.
- 11. Women with child bearing potential and men with reproductive potential must be willing to practice acceptable methods of contraception.
- 12. Ability to understand and the willingness to sign a written informed consent document.
- 13. Willingness to undergo biopsy of metastatic site or site of unresectable disease prior to randomization.

#### 7.2 Exclusion Criteria

Participants meeting any of the following criteria are ineligible to participate in this study:

- 1. Concurrent malignancies:
  - a. Participants with a previously treated malignancy are eligible to participate if all treatment of that malignancy was completed at least 2 years before registration and the participant has no evidence of disease.
  - b. Participants who have a concurrent malignancy that is clinically stable and does not require tumor-directed treatment are eligible to participate if the risk of the prior malignancy interfering with either safety or efficacy endpoints is very low (with agreement from the sponsor and PI).
  - c. Other malignancies may be permitted if the risk of the prior malignancy interfering with either safety or efficacy endpoints is very low (with agreement from the sponsor and PI).
- 2. Any major surgical procedures or external beam radiotherapy within 14 days prior to study drug administration.
- 3. Use of other investigational drugs within 28 days prior to study drug administration.
- 4. Symptomatic or untreated leptomeningeal or brain metastases or spinal cord compression. Treated brain metastases must have been stable for at least 1 month and require treatment with less than 10 mg/day prednisone equivalent for at least two weeks prior to study drug administration.
- 5. Prior exposure to either ipilimumab or combined checkpoint blockade.
- 6. Any diagnosis of autoimmune disease. Participants with Type I diabetes mellitus, hypothyroidism only requiring hormone replacement, adrenal insufficiency on replacement dose steroids, skin disorders (such as vitiligo, psoriasis or alopecia) not requiring systemic treatment, or conditions not expected to recur in the absence of an external trigger are permitted to enroll.
- 7. Pregnant women and lactating women.

- 8. History of uveal melanoma.
- 9. Known Human Immunodeficiency Virus (HIV), Hepatitis B Virus (HBV), or Hepatitis C Virus (HCV) infection (with the exception of chronic or cleared HBV or HCV infection, which will be allowed). Once-documented negative result for HIV, HBV, and HCV is sufficient.
- 10. Uncontrolled intercurrent illness including, but not limited to, ongoing or active infection and psychiatric illness/social situations that would limit compliance with study requirements.
- 11. Participants with a condition requiring systemic treatment with either corticosteroids (>10 mg daily prednisone equivalent) or other immunosuppressive medications within 14 days of study drug administration. Inhaled or topical steroids and adrenal replacement steroid doses >10 mg daily prednisone equivalent are permitted.
- 12. Participants with history of any grade 4 toxicity during previous anti PD-1 treatment or history of Grade 3 or higher pneumonitis.
- 13. Participants with a history of grade  $\geq 2$  neuropathy.
- 14. Prisoners or participants who are involuntarily incarcerated.
- 15. Children under the age of 18.
- 16. Participants who require hemodialysis.
- 17. Participants with a history of allergy to study drug components or history of a severe hypersensitivity reaction to any monoclonal antibody.

# 7.3 Withdrawal, Removal, and Replacement of Participants

A participant may voluntarily withdraw or be withdrawn from the study at any time for reasons including, but not limited to, the following:

- Progression of disease: Either unequivocal symptomatic progression necessitating a change in therapy in the opinion of the treating physician or radiologic progression as defined by cross-sectional imaging utilizing RECIST 1.1 criteria.
- Treatment Cessation: Discontinuation criteria apply for all drug-related AEs attributed to nivolumab, ipilimumab or both. Treatment with all study drugs should be permanently discontinued for the following:
  - Any Grade 2 drug related uveitis or eye pain or blurred vision that does not respond to topical therapy and does not improve to Grade 1 severity within the re-treatment period OR requires systemic treatment
  - o Any Grade 3 non-skin, drug-related AE, with the following exceptions:
    - Grade 3 diarrhea lasting <7 days
    - Grade 3 drug-related laboratory abnormalities do not require treatment discontinuation except
      - ➤ Grade 3 drug-related thrombocytopenia >7 days or associated with bleeding requires discontinuation
      - Any drug-related liver function test abnormality that meets the following criteria requires discontinuation:
        - AST or ALT >8 x upper limit of normal (ULN)
        - Total Bilirubin >5x ULN
        - Concurrent AST or ALT and total bilirubin >2x ULN
  - Any Grade 4 drug-related AE or laboratory abnormality, except for the following events which do not require discontinuation.

- Grade 4 amylase or lipase abnormalities that are not associated with symptoms or clinical manifestations of pancreatitis.
- Isolated Grade 4 electrolyte imbalances/abnormalities that are not associated with clinical sequelae and are corrected with supplementation/appropriate management within 72 hours of their onset
- Any dosing interruption lasting >6 weeks with the following exceptions:
  - Dosing interruptions to allow for prolonged steroid tapers to manage drugrelated AEs are allowed.
  - Dosing interruptions >6 weeks that occur for non-drug related may be allowed if approved by the primary Investigator
- Any AE, laboratory abnormality or intercurrent illness which, in the judgment of the Investigator, presents a substantial clinical risk to the participant with continued drug dosing.
- Withdrawal of consent: Participant may withdraw consent at any time.
- Death
- Screening Failure: If, at any point after enrollment, the PI determines that the participant does not meet all inclusion criteria or meets any exclusion criteria. Rescreening is permitted.

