## 7.4 Follow-Up for Drug Discontinuation/Participant Withdrawal from Study

If a participant discontinues study treatment and is withdrawn from the study for any reason, the study site must immediately notify the medical monitor. The date and the reason for study discontinuation must be recorded on the electronic case report form (eCRF). Participants who withdraw prematurely are to attend an Early Termination Visit, if possible, and complete all assessments.

In the event that a participant discontinues prematurely from the study due to a treatment-emergent adverse events (TEAE) or serious TEAE, the TEAE or serious TEAE will be followed until it resolves (returns to normal or baseline values) or stabilizes, or until it is judged by the Investigator to be no longer clinically significant.

Once a participant is withdrawn from the study, the participant may not re-enter the study.

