**Table 3: Schedule of Assessments** 

	Baseline/ Screening a	Cycle 1 b	Cycle 2	Cycle 3	Cycle 4	Follow-up Visit 1 and 2 d	Additional Follow-up Visits e	Early Termination Visit f
Obtain Informed Consent	X							
Participant History	X							
Inclusion/Exclusion criteria	X							
Biopsy of Target Lesion c	X	X						
Prior/concomitant medications	Collected from Screening to Follow-up							
Physical Examination	X	X	X	X	X	X		X
Performance status	X	X	X	X	X	X		X
Height/Weight	X	X	X	X	X	X		X
Vital Signs	X	X	X	X	X	X		X
Complete Blood Count	X	X	X	X	X	X		X
Complete Metabolic Panel, LDH	X	X	X	X	X	X		X
Thyroid function testing g	X	X	X	X	X	X		X
Pregnancy test (serum)	X	X	X	X	X	X		X
HCV, HBV, HIV Testing	X							
CT scan h	X				X	X		X
MRI Brain	X							
ECG	X							
Adverse Events	Collected from consent to 100 days after drug discontinuation							
Drug Administration		X	X	X	X			
Research blood (~40mL)	X	X	X	X	X	X		X

PD-L1 expression on banked tumor specimen if available	X					
Survival Data				X	X	X

<sup>aScreening assessments are recommended to be performed within 28 days prior to treatment unless otherwise specified above

<sup>bEach cycle=21 days±4 days

<sup>cBiopsy at baseline for all participants within 14 days of Cycle 1, Day 1. On-treatment biopsy must be performed within 14 days±5 days of first dose of study drug.

<sup>dFollow up period begins when the last dose of study therapy is administered. Follow-up visit 1=21 days from last dose  $\pm$  7 days. Follow-up visit 2=42 days from last dose  $\pm$  7 days. If the participant completed follow-up visit 1 and follow-up visit 2 and *has* progressed, the participant is not required to have scans every 12 weeks. Survival could be assessed via calls every 3 months ( $\pm$ 7 days). If a participant is off treatment and *has not* progressed, they would continue to visit the site and have scans every 12 weeks.

 $^{\rm e}$ Additional follow-up visits will be scheduled every 3 months  $\pm 7$  days. For participants who end treatment for toxicity, scans should continue every 12 weeks until progression of disease. After progression of disease, survival calls will occur every 3 months ( $\pm 7$  days).

<sup>fFor participants who terminate the study early, follow-up will begin 21 days from the last dose (follow-up visit 1).

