#### **10.1.4 Repeat Evaluations**

Repeat Evaluations are periodic measurements of disease burden must be assessed utilizing the same cross-sectional imaging modalities as baseline. Participants who do not undergo repeat assessments within acceptable time frames will be removed from study and censored at the time of last evaluation.

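### Protocol 10.1.4 and 7.3/7.4 conflict with Table 3, section 9.1 and SAP 5.4.2 on whether participants who miss scans, progress or stop drug stay in OS and TTF follow-up

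*Protocol*

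**What the plan says.** **Text that takes participants out of the study**

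- Protocol 7.3 opens with "A participant may voluntarily withdraw or be withdrawn from the study at any time for reasons including, but not limited to, the following". The list includes disease progression, treatment cessation, withdrawal of consent, death and late-found ineligibility ("If, at any point after enrollment, the PI determines that the participant does not meet all inclusion criteria"). Under treatment cessation the directive wording concerns drug only: "Treatment with all study drugs should be permanently discontinued for the following".
- Protocol 7.4: "Once a participant is withdrawn from the study, the participant may not re-enter the study". It asks for an Early Termination Visit and follow-up of adverse events, and does not mention survival.
- Protocol 10.1.4: "Participants who do not undergo repeat assessments within acceptable time frames will be removed from study and censored at the time of last evaluation". No endpoint is named, and the acceptable time frames are not defined.

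**Text that keeps them in**

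- Table 3, footnote e: "For participants who end treatment for toxicity, scans should continue every 12 weeks until progression of disease", and then "After progression of disease, survival calls will occur every 3 months". Footnote d says, more weakly, that survival could be assessed by calls in progressors. Footnote f starts follow-up 21 days after the last dose for those who terminate early.
- Protocol 9.1 provides for remote contact for OS data for up to 2 years.
- SAP 5.4.2 censors OS at last contact and TTF at last follow-up. It has no rule that censors at progression, drug stopping or a missed scan.

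**Related SAP text.** SAP 3.5 accepts early discontinuation from the study as an end of follow-up. SAP 5.4 includes data after drug stopping from participants who continued assessments. SAP 5.4.4 plans no sensitivity analysis. SAP section 6 does not list 10.1.4 among the differences from the protocol.

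**The concern.** Section 7.3 mixes two decisions in one list: ending study drug and ending study participation. Section 10.1.4 then makes a missed assessment a compulsory exit. A site cannot both remove a participant under 10.1.4 and go on making the calls in Table 3.

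The SAP takes precedence for the analysis, but it can only use data that were collected. If contact stops at removal, the date of last contact is the removal date, and the SAP rule censors there.

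That censoring is informative if the people removed have a higher risk of death than those who stay. This is plausible at progression. TTF is exposed in a second way. Its event is new systemic therapy or death, and the progression ground in 7.3 includes symptomatic progression that calls for a change of therapy. Withdrawal at that moment would censor TTF just before its event. Also, the Additional Follow-up column of Table 3 marks survival data but has no explicit item for subsequent therapy.

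**Working it through.** **1. Is there a plan figure to reproduce?** No. Neither document states an expected OS or TTF, an event count or a withdrawal rate. The size can only be illustrated.

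**2. The passages side by side**

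| Event | Exit text | Follow-up text | Is censoring ordered? |
|---|---|---|---|
| Missed repeat assessment | 10.1.4, mandatory | 9.1 (OS contact for up to 2 years) | Yes, endpoint unnamed |
| Progression | 7.3, permissive | Table 3 footnotes d and e; 9.1 | No |
| Drug stopped for toxicity | 7.3, permissive on leaving the study, directive on drug | Table 3 footnote e; 9.1 | No |
| Early termination | 7.4, no re-entry | Table 3 footnote f; 9.1 | No |
| Late-found ineligibility | 7.3, permissive | 9.1; analysis sets in SAP 5.1 | No |

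**3. Illustration: withdrawal at progression.** All rates in this step are assumptions. Take three states: before progression, after progression, and dead. Let λ be the progression hazard, d0 and d1 the death hazards before and after progression, and a = λ + d0.

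- Before progression: P0(t) = exp(−a·t)
- After progression: P1(t) = λ·[exp(−d1·t) − exp(−a·t)] / (a − d1)
- True OS(t) = P0(t) + P1(t)
- If a share q of progressors is censored at progression, the hazard that Kaplan-Meier sees is h(t) = [P0·d0 + (1−q)·P1·d1] / [P0 + (1−q)·P1], and the estimate tends to exp(−∫h).

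With a median of 3 months to progression, λ = ln 2 / 3 = 0.231 per month. For d0 = 0.01 and d1 = 0.10 per month, at 12 months P0 = 0.055 and P1 = 0.403, so true OS is 45.8%.

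| d0 / d1 per month | True 12-month OS | q = 25% | q = 50% | q = 100% |
|---|---|---|---|---|
| 0.01 / 0.10 | 45.8% | 48.6% (+2.8) | 52.9% (+7.1) | 88.7% |
| 0.02 / 0.08 | 50.0% | 51.9% (+1.9) | 54.9% (+4.9) | 78.7% |

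The last column can be checked by hand. With every progressor censored only d0 remains: exp(−0.12) = 88.7% and exp(−0.24) = 78.7%.

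**4. Sensitivity to the assumed rates.** Here d1 is solved so that median OS is 10.1 months, the ipilimumab-alone figure in Protocol 4.2. That figure comes from previously treated patients who are not described as pretreated with a PD-1 inhibitor, so it only sets a scale.

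| Median time to progression; d0 | True 12-month OS | q = 25% | q = 50% |
|---|---|---|---|
| 3 months; 0.005 | 41.2% | 44.5% (+3.3) | 49.9% (+8.7) |
| 3 months; 0.02 | 41.8% | 44.2% (+2.4) | 47.9% (+6.1) |
| 6 months; 0.005 | 41.2% | 47.8% (+6.6) | 57.2% (+16.0) |
| 6 months; 0.02 | 41.5% | 46.1% (+4.6) | 52.6% (+11.1) |

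In every scenario the bias is upward, because d1 exceeds d0. With q = 0, which is what Table 3 and 9.1 provide for, Kaplan-Meier is unbiased in this model.

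**5. Scale against sampling error.** With 12 per arm, one withdrawal is 1/12 = 8% of an arm. A survival proportion near 46% has an approximate 95% half-width of 1.96·√(0.46·0.54/12) = 28 points.

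**6. What this does not cover.** It models withdrawal at progression, which 7.3 permits. It does not model the missed-assessment rule in 10.1.4, which is the only mandatory one. No TTF figure was computed.

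**The case against.** The strongest reply is that the documents already keep these participants in follow-up. Table 3, 9.1 and the SAP censoring rules all point that way, the SAP governs the analysis, and 10.1.4 sits among the RECIST rules, where it may have been meant for a scan-based quantity such as duration of response (listed in Protocol 12.3.2). Footnote d also releases progressors from 12-weekly scans once follow-up visits 1 and 2 are done, so 10.1.4 has little reach after progression. OS and TTF are secondary, nothing is tested, and sampling error exceeds the illustrated bias.

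Most of this stands, and it limits the point to a conflict that could cause bias. It does not remove the conflict: 10.1.4 is mandatory and names no endpoint, and the SAP cannot restore contacts that were never made.

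A reader might infer more than the text supports:

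- *That progression or drug stopping leads to censoring by rule.* Censoring is ordered only in 10.1.4. Section 7.3 is permissive and never mentions it.
- *That the ineligibility clause lets an investigator in an open-label trial remove dosed participants from the analysis.* SAP 5.1.1, 5.1.2 and 5.4 keep everyone dosed, whatever their adherence to the protocol. Only later follow-up is at risk.
- *That the response rate is biased.* SAP 5.4.1 counts participants without a post-baseline assessment as non-responders.
- *That OS could be inflated to 79% or 89%.* This needs every progressor withdrawn, against the Table 3 schedule.
- *That a missed scan, toxicity or ineligibility signals a higher risk of death.* That may be so for some, but the documents give no evidence of it.

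**Conclusion.** The point holds as an unresolved conflict between sections. Following 10.1.4 literally, or using 7.3 to withdraw participants at progression, can end OS and TTF follow-up early and make the censoring informative. The favourable direction is probable for withdrawal at progression, because it rests on death being more frequent after progression than before. For the other grounds the direction is not established.

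If 25% to 50% of progressors were withdrawn, the two sets of rates in step 3 overstate 12-month OS by about 2 to 7 points, and the calibrated sets in step 4 by about 2 to 16. The withdrawal share and all the rates are assumptions. The effect is confined to secondary, descriptive endpoints, and with 12 per arm it would be hard to see in the data. That is a reason to settle it in the text, and an amendment is worth making because it costs little.

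**What to change.** 1. **Protocol 7.3:** split the list in two. Reasons to stop study treatment keep their present clinical criteria unchanged. Reasons to leave the study are withdrawal of consent for follow-up, loss to follow-up, and death.
2. **Protocol 10.1.4:** delete the removal from study. Limit the censoring to a named scan-based endpoint, such as duration of response, and define the acceptable time frames. SAP 5.4.2 has no duration-of-response analysis at present, so add one if that endpoint is named. State that participants who miss assessments stay in follow-up for survival and subsequent systemic therapy for up to 2 years.
3. **Table 3:** add an item for new systemic therapy to the additional follow-up visits, and bring footnote d into line with the firmer wording of footnote e on survival calls.
4. **SAP section 6:** record the change, so that the censoring rules in 5.4.2 clearly replace 10.1.4 for OS and TTF.

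No change is needed to the analysis sets or the non-responder rule. The cost is a wording amendment and a few more of the 3-monthly calls already scheduled, with one added question on new therapy at each.
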